5.1. Overall Design

Study AMBG is a Phase 3, multicenter, randomized, double-blind, placebo-controlled, parallel-arm study evaluating the safety and efficacy of 200 mg mirikizumab Q4W SC in maintaining treatment response at Week 40 (that is, 52 weeks of continuous therapy). The study also will evaluate the safety and efficacy of: (a) extended induction with 300 mg mirikizumab IV for patients who did not have a clinical response at Week 12 of Study AMAN, and (b) rescue induction for patients who achieved clinical response in Study AMAN and subsequently lose clinical response during Study AMBG.

Patient Population

Patients with moderately to severely active UC who completed Study AMAN and who meet eligibility requirements will enroll in this study. The study will enroll patients who achieve clinical response or clinical remission with blinded mirikizumab or placebo dosing in Study AMAN, as well as patients who do not achieve clinical response with blinded mirikizumab or placebo during Study AMAN.

Treatment Assignments

Maintenance study treatment assignment will be dependent on whether patients responded to study drug dosing in AMAN and whether they experience a loss of response (LOR) during this study as follows:

- **Mirikizumab Responders from Study AMAN**

Patients who achieve clinical response with blinded mirikizumab in induction Study AMAN will be randomized to receive blinded 200 mg mirikizumab Q4W SC or blinded placebo SC Q4W (randomized withdrawal) in a 2:1 ratio. Randomization will be stratified to achieve between-group comparability, based on biologic-failed status (yes or no), induction remission status (yes or no), baseline corticosteroid use (yes or no), and region (North America/Europe/Other).

Patients will continue on the randomized treatment assignment for the remainder of Study AMBG unless they develop secondary LOR.

Loss of Response (LOR) is defined as:

- ≥ 2 -point increase from Study AMBG baseline in the combined SF + RB scores AND combined SF + RB score of ≥ 4 , on 2 consecutive visits (≥ 7 days apart), and with confirmation of negative *C. difficile* testing (first assessment can start as early as Week 8/Visit 3),

AND

- Confirmed by centrally read endoscopic subscore (ES) of 2 or 3 not sooner than Week 12/Visit 4.

SC dosing should be continued according to dosing schedule until endoscopy determines whether LOR is confirmed. If LOR is confirmed based on endoscopy at or after Week 12 (and *C. difficile* stool toxin testing is negative), patients will be rescued with open-label 300 mg mirikizumab Q4W IV for 3 doses. The first IV rescue dose may be administered as soon as LOR is confirmed by centrally read endoscopy, if ≥ 7 days from the most recent SC dose. Subsequent doses will be given every 4 weeks for total of 3 doses.

If endoscopy does not confirm secondary LOR, patients are encouraged to continue SC study drug dosing, maintaining the scheduled dosing interval. If study drug dosing is continued, an additional endoscopy would be performed at Week 40, early termination visit (ETV) or unscheduled visit (UV).

Patients who, in the opinion of the investigator, receive clinical benefit after completion of the LOR rescue therapy (12 weeks after first IV rescue dose) may be considered for enrollment into the long term extension study I6T-MC-AMAP (AMAP) to receive further SC dosing. Once the LOR IV rescue therapy is initiated, no further SC dosing will be available in AMBG.

If study drug is discontinued, procedures for early termination from study drug will be performed and the patient should undergo post-treatment follow-up as described in the schedule of activities (Section 2).

- **Placebo Responders from Study AMAN**

Patients who achieve clinical response with blinded placebo in the induction study will continue to receive blinded placebo for the remainder of the maintenance study. Placebo SC injections will be administered Q4W to maintain study blind. If LOR is confirmed based on endoscopy at or after Week 12 (and *C. difficile* stool toxin testing is negative), patients will be rescued with open-label mirikizumab 300 mg Q4W IV for 3 doses. The same LOR assessments and procedures should be performed as described for the mirikizumab responders from Study AMAN.

- **Mirikizumab and Placebo Nonresponders from Study AMAN**

Patients who do not achieve clinical response to blinded mirikizumab or blinded placebo in Study AMAN will receive open-label extended induction therapy with 300 mg mirikizumab IV at Weeks 0, 4, and 8, and undergo endoscopy at Week 12.

Patients who achieve delayed clinical response (compared to induction study baseline) with extended mirikizumab induction therapy at Week 12 may subsequently receive open-label 200 mg mirikizumab Q4W SC starting at Week 12. Patients will continue on this dose regimen and undergo endoscopy at Week 40. Patients who, in the opinion of the investigator, receive clinical benefit may be considered for enrollment into the long term extension study AMAP to receive further SC dosing. Patients who discontinue study drug before Week 40 will undergo endoscopy and procedures for early termination of the study drug, including post-treatment follow-up as described in the schedule of activities (Section 2).

Patients who do not achieve clinical response to mirikizumab IV extended induction therapy at Week 12, compared to induction baseline, will discontinue study drug and undergo procedures for early termination of the study drug, including post-treatment follow-up as described in the schedule of activities (Section 2).

Post-Treatment Follow-up Period

Patients will undergo a maximum 16-week post-treatment follow-up period:

- Patients who discontinue study drug with **last dose administered IV** will return for post-treatment follow-up visits (Visit 801 and 802) at 4 and 16 weeks after the end-of-treatment visit.
- Patients who discontinue study drug with **last dose administered SC** will return for post-treatment follow-up visits (Visit 801 and 802) at 4 and 12 weeks after the end-of-treatment visit.
- Patients who subsequently enter the long term extension study AMAP do not need to complete the post-treatment follow-up period.

Figure AMBG.5.1 illustrates the study design. Study governance considerations are described in detail in Appendix 3.

[figure not shown]

Figure AMBG.5.1. Illustration of study design for Clinical Protocol I6T-MC-AMBG.

Footnotes for Figure AMBG.5.1

Abbreviations: D/C = discontinue; IV = intravenous; LOR = loss of response; Miri = mirikizumab; OL = open-label; PBO = placebo; Q4W = every 4 weeks; R = randomization; RB = rectal bleeding; SC = subcutaneous; SF = stool frequency; W = week.

Note: LOR is defined as ≥ 2 -point increase from maintenance baseline in the combined SF + RB scores, AND combined SF + RB score of ≥ 4 on 2 consecutive visits, AND confirmed by an endoscopic subscore of 2 or 3.

a = Loss of response at or after Week 12 and up to and including Week 28.

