Rescue mirikizumab IV dosing																	X ^d : Three Q4W IV rescue doses administered instead of SC dosing, if secondary loss of response (LOR) is confirmed. The IV dosing must start no later than V8/Week 28. The IV dosing visit window may shift if first rescue dose is given outside of SC dosing visit window. Rescue IV doses to be given Q4W with visit window tolerance of +/- 3 days.
Physical Examination																	
Vital signs (T, BP, and PR)	X	X	X	X	X	X	X	X	X	X	X	X	X	X	X	X	
Weight	X ^c						X				X	X					

Procedure	Randomized Maintenance Period												Post-treatment Follow-up		Notes		
	V1	V2	V3	V4	V5	V6	V7	V8	V9	V10	V11	N/A	V997	801		802	
Visit	V1	V2	V3	V4	V5	V6	V7	V8	V9	V10	V11	N/A	V997	801	802		
Week	0	4	8	12	16	20	24	28	32	36	40 LV	ETV	UV	LV or ETV +4	LV or ETV +12/16 ^b		
Day and/or Visit Interval Tolerance	1 ^a	29 +/-7	57 +/-7	85 +/-7	113 +/-7	141 +/-7	169 +/-7	197 +/-7	225 +/-7	253 +/-7	281 +/-7	N/A	N/A	+/-10	+/-10		
Physical examination	X ^c			X ^d								X	X	X ^d			X ^d : A targeted physical exam to be performed as appropriate for patients with secondary LOR.
Evaluate for EIMs	X	X	X	X	X	X	X	X	X	X	X	X	X			See Section 9.1.3.2.	
12-lead ECG	X ^c										X	X					
Laboratory Investigations																	
Urine pregnancy test	X	X	X	X	X	X	X	X	X	X	X	X	X	X	X	Only in women of childbearing potential. Done locally and prior to dosing.	
HBV DNA ^d	X ^{c,d}			X ^d			X ^d				X ^d	X ^d				X ^d : For patients who were HBsAg-, anti-HBc+, and HBV DNA not detected in Study AMAN. See Section 9.4.5.2.	
Hematology	X ^c	X	X	X	X	X	X	X	X	X	X	X	X	X	X		
Chemistry	X ^c	X	X	X	X	X	X	X	X	X	X	X	X	X	X		
Fasting lipid profile ^e	X ^c										X	X					
hsCRP ^e	X ^c										X	X					
FSH (optional in women to confirm nonchild-bearing potential) ^e		X														Optional, to confirm post-menopausal status in women ≥50 years with amenorrhea for >1 year.	
Serum and plasma for cytokines	X ^c						X				X	X					

Procedure	Randomized Maintenance Period												Post-treatment Follow-up		Notes	
	Visit	V1	V2	V3	V4	V5	V6	V7	V8	V9	V10	V11	N/A	V997		801
Week	0	4	8	12	16	20	24	28	32	36	40 LV	ETV	UV	LV or EIV +4	LV or EIV +12/16	
Day and/or Visit Interval Tolerance	1 ^a	29 +/-7	57 +/-7	85 +/-7	113 +/-7	141 +/-7	169 +/-7	197 +/-7	225 +/-7	253 +/-7	281 +/-7	N/A	N/A	+/-10	+/-10	

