7.4. Dosage Modification

Dose adjustments, other than the dose regimen change provided to patients who demonstrate a LOR, described in Section 7.1, are not permitted in this study.

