9.1. Efficacy Assessments

Table AMBG.9.1. Endpoint Definitions in Study AMBG

Endpoint	Definition
Clinical remission	
 Stool frequency (SF) subscore = 0, or SF = 1 with a ≥ 1-point decrease from induction baseline, and Rectal bleeding (RB) subscore = 0; and Endoscopic subscore (ES) = 0 or 1 (excluding friability)
Clinical remission (using a more stringent ES)	
 SF subscore = 0, or SF = 1 with a ≥ 1-point decrease from induction baseline, and RB subscore = 0; and ES = 0
Clinical response	
 A decrease in the modified Mayo score (MMS) of ≥ 2 points and $\geq 30\%$ decrease from baseline, and A decrease of ≥ 1 point in the RB subscore from baseline or a RB score of 0 or 1
Corticosteroid-free remission without surgery at Week 40^a	
 Clinical remission at Week 40, and Symptomatic remission at Week 28, and No corticosteroid use for ≥ 12 weeks prior to Week 40
Endoscopic remission	
 ES = 0 or 1 (excluding friability)
Endoscopic response	
 A decrease in the ES of ≥ 1 point compared to baseline
Histologic remission	
 This definition will be specified in the SAP
Mucosal healing	
 Histologic remission as described in the SAP and endoscopic remission defined as ES = 0 or 1 (excluding friability)
Symptomatic remission	
 SF = 0, or SF = 1 with a ≥ 1-point decrease from induction baseline, and RB = 0
Stable maintenance of symptomatic remission^b	
 Symptomatic remission for at least 7 out of 9 visits from Week 4 to Week 36 Symptomatic in remission at Week 40
Bowel movement urgency improvement	
 The definition will be specified in the study SAP

Abbreviations: ES = endoscopic subscore; MMS = modified Mayo score; RB = rectal bleeding; SAP = statistical analysis plan; SF = stool frequency.

^a Among patients induced into clinical response with mirikizumab during the induction study and who were receiving corticosteroids at induction baseline.

^b Among patients in symptomatic remission at Week 12 of Study AMAN.

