9.1.1.3. Endoscopy

Endoscopy will be used to determine the Mayo ES at the time points described in the Schedule of Activities (Section 2).

Flexible sigmoidoscopy is the standard endoscopic procedure for assessment of endoscopic disease activity in this study. However, colonoscopy can be performed instead of flexible sigmoidoscopy within this study in order to surveil for dysplasia, screen for colorectal cancer (see Inclusion Criterion [5]), or for other clinically indicated reasons, in the judgement of the investigator and after discussion with the medical monitor as appropriate.

Endoscopic disease activity assessed at Week 12 of Study AMAN will serve as the baseline assessment of endoscopic disease activity in Study AMBG.

In patients who enter Study AMBG in clinical response or clinical remission, endoscopy will be performed at Week 40, ETV, UV, or if LOR is suspected in these patients based on SF/RB scores, endoscopy can be performed at or after Week 12 to confirm secondary LOR. Secondary LOR must be confirmed endoscopically before rescue mirikizumab IV induction dosing is initiated. If endoscopy does not confirm secondary LOR, patients are encouraged to continue study drug dosing. If study drug dosing is continued, an additional endoscopy would be performed at Week 40, ETV, or UV.

In patients who enter Study AMBG as induction study nonresponders, endoscopy will be performed at Week 12, following extended mirikizumab IV induction. An additional endoscopy will be performed at Week 40, ETV, or UV. Patients who plan to continue in the long term extension study AMAP and who require an annual surveillance colonoscopy to remain up-to-date in screening for colorectal cancer (see Inclusion Criterion [5]), will undergo colonoscopy as the endoscopy method at Week 40.

If a patient becomes pregnant during the study, no additional endoscopies will be performed.

If a patient undergoes early termination soon after baseline, loss of response, or at the end of extended induction endoscopy, the need for ETV endoscopy should be discussed with the medical monitor.

The endoscopy report and histopathology report (if biopsies are sent to a local histopathology laboratory) must be available in the source documents.

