10.3.3. Efficacy Analyses

10.3.3.1. Primary Analyses

The primary endpoint is the proportion of patients with clinical remission at Week 40 (Week 52 of continuous therapy) among the patients who are responders to 300 mg mirikizumab IV at 12 weeks of induction dosing.

For study visits that include endoscopy as a study procedure (for example, Visit 11 [Week 40]), the SF and RB subscores of the Mayo score will be calculated from daily electronic diary data by averaging the most recent 3 valid days (possibly nonconsecutive) in the 7 days prior to commencing bowel preparation for endoscopy. At other study visits, where endoscopy is not performed, SF and RB subscores will be calculated from the daily electronic diary data by averaging the most recent 3 valid days (possibly nonconsecutive) in the 7 days prior to that study visit. If data for fewer than 3 valid days are available, the subscores will be considered missing. Patient diary data obtained on the following days will be excluded: (i) days when bowel preparation was taken prior to endoscopy, (ii) the day of the endoscopy, and (iii) the day after the endoscopy.

Rates of clinical remission at Week 40 among induction responders will be analyzed. Patients who do not achieve clinical remission or who do not reach the Week 40 assessment will be considered to be nonremitters. In addition, patients who take rescue dosing with mirikizumab will be considered nonremitters.

The primary endpoint analysis will utilize the CMH test as described in Section 10.3.1.

Additional analyses of the primary endpoint may be considered and will be fully detailed in the SAP.

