Severe disease	3
Mayo Score = Stool Frequency (SF) + Rectal Bleeding (RB) + Endoscopic Subscore (ES) + Physician's Global Assessment (PGA)	

Note: The Mayo score ranges from 0 to 12, with higher scores indicating more severe disease. Modified Mayo score excludes PGA and ranges from 0 to 9. Composite SF and RB score ranges from 0 to 6. The original description of the Mayo score included friability in the definition of an ES of 1. Consistent with current clinical practice and regulatory guidance, this study excludes friability from the definition of an ES of 1.

Stool frequency reports the number of stools in a 24-hour period, relative to the normal number of stools for that patient. The reference "normal" stool frequency for that patient will be recorded electronically at the screening visit in Study AMAN. The Normal SF refers to when the patient was in remission or, if the patient has never achieved remission, the reported SF before initial onset of signs and symptoms of ulcerative colitis. Remission refers to a period of time since being diagnosed with ulcerative colitis when the patient is not experiencing any signs or symptoms relating to ulcerative colitis. This period of time may last a few weeks or a few months or may even last several years. The patient will record this electronically as source data in the tablet device at the screening study visit in Study AMAN.

Source: Adapted from Schroeder et al. (1987) and Scherl et al. (2009)

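### A clinical responder who enters AMBG with a combined SF+RB score of 5 can never meet the loss-of-response rule, because it would require 7 on a 0-6 scale, and so has no route to IV rescue

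*Protocol*

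**What the plan says.** Section 5.1 gives the symptom part of LOR as a 2-or-more "point increase from Study AMBG baseline in the combined SF + RB scores AND combined SF + RB score of" 4 or more, on two consecutive visits at least 7 days apart with a negative C. difficile test. A centrally read ES of 2 or 3, at Week 12 or later, must confirm it. The note to Figure AMBG.5.1 and the footnote to Table AMBG.7.1 repeat the rule without an exception for a high entry score. The note in Appendix 6 gives the ceiling: "Composite SF and RB score ranges from 0 to 6".

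LOR is the gate to rescue. Section 9.1.1.3 says "Secondary LOR must be confirmed endoscopically before rescue mirikizumab IV induction dosing is initiated", and Section 7.4 says that dose adjustments "other than the dose regimen change provided to patients who demonstrate a LOR, described in Section 7.1, are not permitted". Table AMBG.2.1 closes the window: "The IV dosing must start no later than V8/Week 28". Section 5.1 describes what the provision is for: "rescue induction for patients who achieved clinical response in Study AMAN and subsequently lose clinical response during Study AMBG".

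Clinical response (Table AMBG.9.1) needs a fall in the modified Mayo score (MMS) of at least 2 points and at least 30%. It also needs a fall of at least 1 "point in the RB subscore from baseline or a RB score of 0 or 1".

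**The concern.** A rule based on a rise from baseline, applied to a bounded scale, cannot be met once baseline plus the required rise passes the ceiling. Here that happens for any entry score above 4. Whether it matters depends on whether a patient can be a clinical responder and still enter above 4. If so, the protocol has responders for whom LOR is impossible by arithmetic, although the rescue is described as being for responders who lose their response. The question is one of access to rescue during randomized withdrawal: a patient re-randomized to placebo could return to the worst possible scores and still not count as having lost response.

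**Working it through.** Scores are written SF/RB/ES, each an integer from 0 to 3, and MMS is their sum.

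**Step 1, the ceiling.** The maximum of SF+RB is 3 + 3 = 6, which agrees with Appendix 6.

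**Step 2, the score needed for LOR.** The needed SF+RB is the larger of (entry + 2) and 4.

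| Entry SF+RB | Needed | Reachable (6 or less)? |
|---|---|---|
| 0, 1 or 2 | 4 | yes |
| 3 | 5 | yes |
| 4 | 6 | yes, at the ceiling |
| 5 | 7 | no |
| 6 | 8 | no |

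**Step 3, which responders can enter above 4.**
- Week 12 RB of 3 always fails the RB part of clinical response: it is not 0 or 1, and it cannot be a fall from a maximum of 3. That rules out entry at 6 and the SF 2/RB 3 form of entry at 5.
- This leaves SF 3/RB 2. Because RB 2 is not 0 or 1, RB must have fallen by at least 1, so induction RB was 3.
- Week 12 MMS is 5 + ES, and must be no more than 70% of induction MMS.
 - Induction MMS 9: 0.7 × 9 = 6.3, so ES is 0 or 1.
 - Induction MMS 8: 0.7 × 8 = 5.6, so ES is 0.
 - Induction MMS 7: 0.7 × 7 = 4.9, which is below 5, so none.

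The barred patterns are therefore these four:

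| Induction | Week 12 | MMS | Fall |
|---|---|---|---|
| 3/3/3 | 3/2/1 | 9 to 6 | 3 points, 33% |
| 3/3/3 | 3/2/0 | 9 to 5 | 4 points, 44% |
| 3/3/2 | 3/2/0 | 8 to 5 | 3 points, 37.5% |
| 2/3/3 | 3/2/0 | 8 to 5 | 3 points, 37.5% |

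**Step 4, how many patterns there are in all.** Enumerating every integer induction-to-Week-12 pair against Table AMBG.9.1 gives 869 responder patterns when induction MMS is at least 4, and 915 with no lower limit. AMBG does not state the induction entry score, so the limit of 4 is an assumption. The four barred patterns are the same either way.

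**Step 5, other routes to rescue.** Sections 5.1, 7.1, 7.4 and 9.1.1.3 offer none. The investigator-judged loss of clinical benefit in Section 8.1.1 is written for induction nonresponders on open-label SC dosing, and it leads to discontinuation.

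**Step 6, a cap at 6.** With the needed score set to the smaller of the present value and 6:
- Nothing changes for entry at 4 or below.
- Entry at 5 needs 6.
- No responder meets the clause at entry, because the highest responder entry is 5.
- An SF+RB of 6 means RB 3, which cannot coexist with clinical response.
- A full return to induction scores meets the clause in 3 of the 4 patterns. The exception is 2/3/3, where the induction SF+RB was itself only 5.

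**The case against.** The strongest case against is about weight.

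- **The group is clinically odd.** All four patterns combine maximal stool frequency and RB 2 with ES 0 or 1. In none did SF improve, and in one SF+RB was 5 both before and after induction. Nothing in the protocol shows that such a patient exists. This stands, and it limits the point to a minor one.
- **The patients are not trapped.** Section 7.7 says that UC medication, even if prohibited, should not be held back where the investigator judges that safety would suffer; study drug is then discontinued. Corticosteroids may return to the induction-baseline dose, the patient may stop at any time, and those who complete Week 40 are assessed for AMAP. IV rescue is in any case closed to every responder after Week 28. This also stands. A reader might infer that relapsed patients are left without treatment, and the protocol does not support that.
- **Fractional scores.** Section 10.3.3.1 forms SF and RB by "averaging the most recent 3 valid days (possibly nonconsecutive) in the 7 days prior to that study visit", so a reader might infer that entries of 4.33 and 4.67 are barred as well, and that the group is much larger. That would follow only if the averages are left unrounded. Section 9.1.1.2 defers the details of diary analysis to the SAP, and the protocol describes each subscore on a 4-point scale. The wider reading is therefore not part of this point.
- **The remedy is a clinical choice.** Accepting 6 for entry at 5 accepts a 1-point rise where others need 2. That is true and should be stated.

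None of this answers the arithmetic. A patient entering at 4 who reaches 6 with ES 3 can be rescued; one entering at 5 with ES 0 or 1 who reaches the same state cannot. The protocol gives no reason for the difference.

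**Conclusion.** The point holds for entry at SF+RB 5: LOR, and with it IV rescue, is impossible as written. Entry at exactly 4 is not barred, since 6 can be reached.

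The size is 4 of 869 integer responder patterns, on the assumption of an induction MMS of at least 4. Pattern counts give equal weight to common and rare states, so they are not a patient frequency. The number of patients is not derivable, is probably very small and may be zero.

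A reader might infer bias or lost power in the primary comparison. The protocol does not support that: under Section 10.3.3.1 a rescued patient and an unrescued patient in relapse at Week 40 are both nonremitters. The loss is confined to in-study IV rescue in the Week 12-28 window. Severity: a minor point to consider.

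**What to change.** In Section 5.1, the Figure AMBG.5.1 note and the Table AMBG.7.1 footnote, add for induction responders only: *or, if AMBG-baseline SF+RB is greater than 4, an SF+RB score of 6*. Keep the two consecutive visits at least 7 days apart, the negative C. difficile test, the centrally read ES of 2 or 3 and the Week 12-28 window. State that the use of the LOR criteria for induction nonresponders in Section 8.1.1 is unchanged, since there they lead to discontinuation.

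The amendment should say openly that entry at 5 then needs only a 1-point rise. It should also say that the clause removes the impossibility only at the scale maximum, so a relapse that stops short of 6 still gets no rescue. A lower threshold would be a separate clinical judgement and is not asked for here.

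The cost is wording in three places and a change to the sites' LOR calculation. There may also be a few extra LOR work-ups (stool tests and an endoscopy with biopsies). Each confirmed case adds PK and ADA samples and three open-label infusions, which carry the hypersensitivity risk described in Section 3.3.
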